# 9.1.2. Relationship to Study Drug

The relationship of each AE to the Study Drug will be based on the Investigator's assessment as to whether there is a reasonable possibility the AE was caused by the Study Drug.

The causal relationship between an AE and the study drug will be categorized as two cases in the CRFs as follows:

### Case 1:

- Unlikely Related,
- Possibly Related, and
- Probably Related.

[figure not shown]
The missing relationship to study drug of an AE will be imputed to "Probably Related".

Treatment-related TEAEs are defined as the TEAEs with relationship to study drug is "Possibly Related" or "Probably Related".

#### Case 2:

- Not Related, and
- Reasonable Possibility.

The missing relationship to study drug of an AE will be imputed to "Reasonable Possibility".

Treatment-related TEAEs are defined as the TEAEs with relationship to study drug is "Reasonable Possibility".

For the analysis purposes (regardless of protocol amendment version), treatment-related TEAEs are defined as the TEAEs with relationship to study drug is "Possibly Related" or "Probably Related" or "Reasonable Possibility".

#### 9.1.3. Serious Adverse Events

A Serious Adverse Event (SAE) includes (but is not limited to) an experience occurring at any dose that results in any of the following outcomes:

[figure not shown]
- Death,
- Life-threatening,
- In-patient hospitalization,
- A persistent or significant disability/incapacity,
- A congenital anomaly/birth defect, and
- Other medically important event

#### 9.1.4. Summaries of Adverse Events

An overall summary of TEAEs will be provided by treatment. This summary will present number and percentage of participants with TEAEs per the following classifications:

- Participants with any TEAEs
- Participants with Treatment-Emergent Drug-Related AEs
- Participants with Treatment-Emergent AEs by Maximum Severity as Mild, Moderate, and Severe.
- Participants with TEAE leading to discontinuation from study
- Participants with Treatment-Emergent SAEs
- Participants with Treatment-Emergent SAEs leading to discontinuation from study
- Participants with Treatment-Emergent SAEs resulting in death

The following summary tables for TEAEs will be presented:

- Number and percent of participants reporting treatment-emergent AEs, grouped by MedDRA system organ class and preferred term
- Number and percent of participants reporting treatment-emergent drug-related AEs, grouped by MedDRA system organ class, and preferred term
- Number and percent of participants reporting treatment-emergent AEs, grouped by MedDRA system organ class, preferred term, and maximum severity
- Number and percent of participants reporting treatment-emergent SAEs will be tabulated by system organ class and preferred term and presented by treatment.
- Number and percent of participants reporting treatment-emergent AEs leading to study discontinuation, grouped by MedDRA system organ class and preferred term

For the summary tables above, the SOC terms and PTs will be presented in decreasing order of the total number of participants (frequency) who experienced each AE. System organ class terms and PTs with the same frequency will be presented alphabetically. In the case of multiple occurrences of the same TEAE within the same participant, each participant will only be counted once for each preferred term.

The following data listings for AEs will be provided for each participant by displaying the events captured on the CRF:

- All AEs,
- All serious AEs,
- All AEs leading to study discontinuation, and
- All AEs leading to Death.

In the AE data listings, all AEs will be displayed. AEs that are not treatment-emergent will be flagged in the AE listings.

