# 2.2. Study Endpoints

#### 2.2.1. Safety Endpoints

The safety endpoints of this study include the following:

• Incidence of adverse events (AEs) including treatment-emergent, serious, related to study drug, and leading to withdrawal along with AEs by severity and relationship to study drug.

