# 4. Statistical Analysis and Reporting

# 4.1. Introduction

Data processing, tabulation of descriptive statistics, calculation of inferential statistics, and graphical representations will primarily use SAS (release 9.4 or higher). If the use of other software

is warranted, the final statistical methodology report will detail what software was used for what purposes.

Descriptive summaries of variables will be provided where appropriate. Continuous (quantitative) variable summaries will include the number of subjects (n) with non-missing values, mean, standard deviation (SD), median, minimum, and maximum.

Categorical (qualitative) variable summaries will include the frequency and percentage of subjects who are in the category for each value. In general, the denominator for the percentage calculation will be based upon the total number of subjects in the study population for the treatment group (or cohorts), unless otherwise specified.

The minimum and maximum will be reported with the same degree of precision (i.e., the same number of decimal places) as the observed data. Measures of location (mean and median) will be reported to 1 degree of precision more than the observed data and measures of spread (SD) will be reported to 2 degrees of precision more than the observed data.

Percentages will be presented to 1 decimal place, unless otherwise specified.

This study is considered an exploratory study. Statistical tests will be interpreted in an exploratory sense only and will not be considered formal hypothesis tests.

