#### 6.1.4. Handling of Dropouts or Missing Data

Although every attempt will be made to ensure participants remain in the study to completion and all data is collected as scheduled, the occurrence of missing data cannot be completely prevented.

An incomplete start or stop date of an AE will be imputed as described in section 6.1.8.

Any participant who withdraws from the study will be considered to have missing data at all subsequent visits.

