# 6.1.6. Data Adjustments/Handling/Conventions

[figure not shown]
Only limited data required for analysis will be presented in listings or Clinical Data Interchange Standards Consortium (CDISC) datasets. Analysis results will be presented and summarized in either tables and/or listings. Data not subject to analysis according to this plan will not appear in any tables and listings.

The version 24.0 of the Medical Dictionary for Regulatory Activities (MedDRA) will be used to classify all AEs by system organ class (SOC) and preferred term (PT).

Ongoing AEs from the pivotal studies will be classified as TEAEs in the current study only if they increase in severity on or after the date of the first dose of study drug in the current study. Otherwise, they will be classified as medical history events.

Adverse events with entirely missing start dates will be classified as treatment-emergent, as appropriate.

For partial AE start dates: (a) if only the day is missing, and the month and year match the first dose date and the end date is on or after the first dose date, or AE is ongoing, then the date is assigned the first dose date thus the event will be considered as treatment-emergent; if the month and/or year do not match the first dose date or the end date is prior to the first dose date, then the day is assigned the first day of the month (01); (b) if month or the day and month are missing, and the year matches the first dose date and the end date is on or after the first dose date, or AE is ongoing, then the date is assigned the first dose date; if the year does not match the first dose date

or the end date is prior to the first dose date, then the day/month are assigned the first day of the year (01JAN).

For partial end dates: (a) if only the day is missing, then the day is assigned the last day of the month; (b) if both day and month are missing, they are assigned the last day of the year (31DEC).

Participants will be analyzed by the treatment received for all safety and tolerability assessments.

A treatment related AE is any AE with a relationship to the study drug of "Possibly Related" or "Probably Related" or "Reasonable Possibility".

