# 7. Study Patients/Subjects and Demographics

# 7.1. Disposition of Patients/Subjects and Withdrawals

A summary of the analysis sets includes the number and percentage of subject's rollover and in the safety population. All percentages will be based on the safety population.

The following will be summarized by treatment group:

- Number of participants who enrolled,
- Number and percentage of participants in safety analysis set,
- Number and percentage of participants who completed the study, and
- Number and percentage of participants who discontinued from the study, including the reason for study discontinuation.

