# 7.3. Exposure and Compliance

# 8. Efficacy Analysis

# 8.1. Primary Efficacy Analysis

No applicable Primary Efficacy Analysis is planned.

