# 10. Changes from Planned Analyses

Due to the early sponsor termination of PTI-125-10, the following analyses will no longer be tabulated/listed:

- Mean change in clinical laboratory values from baseline to Weeks 4, 28 and 52
- Mean change in vital signs (blood pressure [supine], temperature, pulse rate) from baseline to Weeks 4, 16, 28, 40, and 52
- Mean change in body weight from baseline to Weeks 4, 16, 28, 40, and 52

- Shifts in physical exam (PE) findings from baseline to Weeks 4, 16, 28, 40, and 52
- Shifts in neurological exam (NE) findings from baseline to Week 4, 16, 28, 40, and 52
- Mean change in ECG parameters from baseline to Weeks 4, 28, and 52
- Concomitant medications/treatments usage
- Shifts in the C-SSRS from baseline to Weeks 4, 16, 28, 40, and 52.
- Shifts in HbA1c values from baseline to Weeks 28 and Week 52. The analysis is done separately among subjects who were previously on placebo and simufilam in PTI-125-06 and PTI-125-07 phase 3 studies.

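### The SAP reports adverse-event incidence only as a percentage of all treated subjects and plans no exposure summary, so with unequal follow-up it cannot be read as a risk over a stated period

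*SAP*

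**What the plan says.** SAP 2.2.1 lists one safety endpoint: "Incidence of adverse events (AEs) including treatment-emergent, serious, related to study drug", with events leading to withdrawal and breakdowns by severity and relationship. SAP 9 adds that safety is judged from reported AEs.

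SAP 9.1.4 says of the overall table: "This summary will present number and percentage of participants with TEAEs per the following classifications". The system organ class and preferred term tables are likewise number and percent of participants. Under SAP 4.1, in general, "the denominator for the percentage calculation will be based upon the total number of subjects in the study population". SAP 5 defines the safety population as everyone with at least one dose.

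SAP 7.3 is titled "Exposure and Compliance" and passes straight to Section 8. The planned tables (SAP 12.1 and 12.2) and listings (12.3) cover disposition, demographics and AEs only. SAP 6.1.6 states: "Data not subject to analysis according to this plan will not appear in any tables and listings".

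On follow-up, SAP 3.1 describes a 52-week study. SAP 6.1.4 says: "Any participant who withdraws from the study will be considered to have missing data at all subsequent visits". SAP 10 opens: "Due to the early sponsor termination of PTI-125-10, the following analyses will no longer be tabulated/listed", and names nine analyses; exposure is not one of them. Protocol Section 4 and Appendix B describe an open-ended study, with drug dispensed at Week 52 and repeat visits afterwards.

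**The concern.** A participant observed for four weeks and one observed for a year count equally in the denominator. When follow-up varies, the percentage mixes the event rate with the length of observation. A reader who wants the risk of, say, a serious event over a year on drug cannot get it from the percentage, and no planned summary shows how long subjects were treated or observed. The objective is long-term safety and this is the only endpoint, so the main result would lack a time base.

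**Working it through.** **1. Is there a figure to reproduce?** No. SAP 3.2 gives no sample-size calculation, and neither document gives an AE rate or a follow-up distribution. The check is a trace of the planned outputs followed by an illustration.

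**2. Trace of outputs.** Three places could supply time at risk.
- SAP 7.3: no text.
- SAP 12: Tables 14.1.1, 14.1.2 and 14.3.1.1 to 14.3.2.3 and the three subject listings contain no exposure, person-time or time-to-event output.
- SAP 7.1: completers are counted, as is "Number and percentage of participants who discontinued from the study, including the reason for study discontinuation". These are counts with reasons, not durations.

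**3. Illustration.** Inputs assumed here, because the documents give none: share p completing 52 weeks, stopping times of the others, and first-event hazard. Take 52 weeks as 1 year.

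F(t) = 1 − exp(−H(t)), where H is the cumulative hazard. Crude percentage = p·F(end of follow-up for completers) + (1 − p)·(mean of F over the others' stopping times).

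Constant hazard of 0.20 per year, p = 0.5, others stopping uniformly over the year:
- F(1) = 1 − e^(−0.2) = 0.1813, the 52-week risk.
- Mean of F over (0, 1) = 1 − (1 − e^(−0.2))/0.2 = 0.0937.
- Follow-up ends at Week 52: 0.5 × 0.1813 + 0.5 × 0.0937 = 0.1375, ratio to the 52-week risk 0.76.
- Completers continue to 104 weeks: F(2) = 1 − e^(−0.4) = 0.3297, so 0.5 × 0.3297 + 0.5 × 0.0937 = 0.2117, ratio 1.17.
- Half the completers continue: 0.25 × 0.3297 + 0.25 × 0.1813 + 0.5 × 0.0937 = 0.1746, ratio 0.96.

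**4. Sensitivity with follow-up ending at Week 52** (p = 0.5 and uniform stopping unless stated).

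| Change | Crude ÷ 52-week risk |
|---|---|
| Constant hazard 0.05 to 0.50 | 0.75 to 0.77 |
| Constant 0.20; p = 0.25 / 0.75 / 0.90 | 0.64 / 0.88 / 0.95 |
| Front-loaded hazard (0.5 for 3 months, then 0.1; same 18.1% risk) | 0.85 |
| Constant 0.20; others stop in months 0–3 | 0.57 |
| Constant 0.20; others stop in months 9–12 | 0.94 |

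The last two rows have the same completion percentage (50%), so that percentage cannot be used to correct the AE percentage.

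**5. Would a person-time rate alone do?** First events divided by mean time at risk gives 0.1375/0.687 = 20.0 per 100 person-years under the constant hazard. Under the front-loaded hazard it is 0.1543/0.661 = 23.4, although the 52-week risk is 18.1% in both cases. The rate is useful but is not a risk.

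**6. Is Week 52 cumulative incidence estimable?** With the SAP's 1081 participants, p = 0.5 and the constant hazard, Greenwood's variance is e^(−2H(1))/n × ∫ h·e^(H(t))/(1 − 0.5t) dt = 0.6703/1081 × 0.311. The standard error is 0.0139 and the 95% half-width about 2.7 percentage points. This ignores competing events and shows only that precision would be adequate under these assumptions.

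**The case against.** The best defence is that the study is single-arm, exploratory and descriptive, and that n (%) is a correct account of what was observed. The SAP never calls the percentage a 52-week risk. All of that stands. It limits the point to how absolute incidence can be interpreted. A reader might infer a between-arm bias or a faulty test, but the plan has one treatment and no formal test, so neither follows.

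A reader might also infer that the percentage understates the yearly risk. The documents do not support a direction. It does so in the illustration only if follow-up stops at Week 52, as in the SAP's design. Under the protocol's open-ended design it can overstate the yearly risk, and the SAP, written to protocol version 3.0, does not say whether later data would enter.

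Listings might be thought to fill the gap. SAP 9 says all safety and tolerability data will be listed, and SAP 12.3 says that in general each CRF domain gets a listing. These pull against SAP 6.1.6, and the conflict should be resolved. Still, Table 4 names no exposure listing, and the content of the disposition listing is not described. AE listings give no time at risk for subjects without events.

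The empty 7.3 might be lost text. The finding does not rest on it, because Section 12 independently contains no exposure output. Nor should the omission be read as a deliberate cut: SAP 10 records no such decision.

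**Conclusion.** The point holds in this form: the sole safety endpoint is planned as a crude percentage with no accompanying measure of exposure or follow-up, in a study that the SAP itself says has withdrawals and was terminated early. The percentage is valid as a count and cannot be read as a risk over a stated period.

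The actual size is unknown. With half completing, uniform stopping and a constant 20 per 100 person-years, the crude figure would be 13.7% or 21.2% against a 52-week risk of 18.1%, depending on whether completers stop at Week 52 or all continue to Week 104. If 90% complete and follow-up ends at Week 52, the ratio is 0.95 and little is lost. Without an exposure summary a reader cannot tell which case applies. This should be corrected, but it does not invalidate the planned tables.

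**What to change.** 1. Write SAP 7.3 and add to Section 12 a table of the distribution of time on drug and total person-years, excluding off-drug gaps. State whether data after Week 52, from continuing or re-entering participants, are included.
2. Keep n (%). Beside it, for any TEAE, SAEs, drug-related TEAEs and TEAEs leading to discontinuation, report cumulative incidence at Week 52, censored at end of follow-up.
   - Count a fatal AE as the event where it meets that category's definition. Treat death as a competing event only otherwise.
   - For TEAEs leading to discontinuation, treat withdrawal for other reasons as competing.
   - State that censoring at withdrawal is assumed independent. This is less secure than censoring at sponsor termination.
3. Optionally add first events per 100 person-years at risk, described as an average rate.

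If re-entry data are analysed, state one consistent at-risk window once the sponsor has reconciled Protocol 7.1.2 (gap conditions as medical history, alongside AE monitoring), 7.1.7 (call 7–14 days after the last dose) and 11.5 (SAEs within 30 days).

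The cost is SAP wording, one table, a few columns and some programming. Protocol Section 10 requires the stop date for discontinued subjects. For others, the last-dose date may have to be derived from visit and drug-accountability records. No new data collection is needed.

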7.1.8. Unscheduled Visits and Discontinuation due to AEs

For unscheduled visits due to AEs, any assessments conducted will be at the discretion of the Investigator and pertinent to the AE. If a decision is made to discontinue the subject from study drug, the Sponsor will be notified immediately. The subject should be followed and treated by the Investigator until the AE has resolved or stabilized (see Section 10 – Adverse Events). Restarting the subject on study drug will be a mutual decision by the Investigator and the Sponsor. See also Section 9 – Early Discontinuation.

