10. EARLY DISCONTINUATION

Subjects may choose to discontinue study drug or study participation at any time, for any reason, and without prejudice. Moreover, a subject may be withdrawn at any time at the discretion of the Investigator or Sponsor for safety, behavioral or administrative reasons. Discontinued subjects should be followed according to medical practice standards, and the outcome documented. Follow-up is required if the subject is discontinued due to an adverse event (AE). Any comments (spontaneous or elicited) or complaints made by the subject and the reason for termination and the date of stopping the drug must be recorded in the Case Report Form (CRF) and source documents.

The following must be completed and documented in the CRFs and source documents for all subjects who discontinue the study early:

- The reason for early study discontinuation. If the subject is withdrawn for more than one reason, each reason should be documented in the source documents and the most clinically relevant reason should be entered on the CRF.
- Vital signs (blood pressure, temperature, and pulse), brief physical and neurologic examination, height, weight, clinical laboratory tests, collection of HbA1c (if collected on Study Day 1 or Re-entry Day 1), plasma biomarkers, ECG, use of concomitant medications, and adverse events should be obtained at discharge prior to release.
- C-SSRS (as detailed in Section 7.1.6 – Early Termination Visit), if not performed within the last 30 days.

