#### 2. Study Objectives and Endpoints

# 2.1. Study Objectives

# 2.1.1. Primary Objective

[figure not shown]
The primary objective of this study is to evaluate the long-term safety and tolerability of simufilam 100 mg tablets in subjects who have completed one of the two double-blind simufilam phase 3 studies.

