# 12.2. Safety Data

**Table 3: Safety Data** 

Table Number	Population Table Title / Summary				
14.3.1 Displays o	14.3.1 Displays of Adverse Events				
Table 14.3.1.1	Safety	Overall Summary of Treatment Emergent Adverse Events			
Table 14.3.1.2	Safety	Summary of Treatment Emergent Adverse Events by System Organ Class and Preferred Term			
Table 14.3.1.3	Safety	Summary of Treatment Emergent Drug-Related Adverse Events by System Organ Class and Preferred Term			
Table 14.3.1.4	Safety	Summary of Treatment Emergent Adverse Events by System Organ Class, Preferred Term, and Maximum Severity			
Table 14.3.1.5	Safety	Summary of Serious Treatment Emergent Adverse Events by System Organ Class and Preferred Term			
Table 14.3.1.6	Safety	Summary of Treatment Emergent Adverse Events Leading to Study Discontinuation by System Organ Class and Preferred Term			
14.3.2 Summary	14.3.2 Summary of Deaths, Other Serious and Significant Adverse Events				
Table 14.3.2.1	Safety	Listing of Serious Adverse Events			
Table 14.3.2.2	Safety	Listing of Adverse Events Leading to Study Discontinuation			
Table 14.3.2.3	Safety	Listing of Adverse Events Leading to Death			

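### The SAP's discontinuation outputs count only AEs that lead to leaving the study, so AE-driven stops of study drug followed by restart, or by an exit recorded under another reason, do not appear in them

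*SAP*

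**What the plan says.** **SAP.** Section 2.1.1 states: "The primary objective of this study is to evaluate the long-term safety and tolerability of simufilam 100 mg tablets". Among the safety endpoints, section 2.2.1 names AEs "leading to withdrawal along with AEs by severity and relationship to study drug". It does not say what the subject withdraws from.

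The outputs settle that question one way:

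- Section 9.1.4, overall summary: "Participants with TEAE leading to discontinuation from study", with a matching row for serious events.
- Section 9.1.4, SOC/PT table: "Number and percent of participants reporting treatment-emergent AEs leading to study discontinuation, grouped by MedDRA system organ class and preferred term".
- Table 3: a summary table with the same scope, and "Listing of Adverse Events Leading to Study Discontinuation".
- Section 7.1, disposition: subjects who left the study, with the reason. It has no line for stopping drug.

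Section 7.3, Exposure and Compliance, is a heading with no text.

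**Protocol.** Section 10 keeps the two events apart: "Subjects may choose to discontinue study drug or study participation at any time". Section 7.1.8 deals with AE-driven decisions about study drug, requires follow-up until the AE resolves or stabilises, and adds: "Restarting the subject on study drug will be a mutual decision by the Investigator and the Sponsor". The stopping criteria in section 7.1.9 that name what is stopped (liver chemistry, C-SSRS) name study drug. For subjects who discontinue, section 10 also requires that "the date of stopping the drug must be recorded in the Case Report Form".

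**The concern.** The endpoint leaves withdrawal undefined, and the tables define it by the event further from tolerability. Stopping the tablets because of an AE is a direct sign that the drug was not tolerated. Leaving the study is a later, administrative event that may or may not follow.

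The discontinuation rows also carry more weight in this SAP than usual. Section 10 drops the laboratory, vital-sign, body-weight, ECG and C-SSRS summaries because the sponsor ended the study early, and section 9 evaluates safety from reported AEs. Only the discontinuation rows show that an AE was bad enough to stop treatment. A subject taken off drug for raised liver enzymes who later restarted would appear as an ordinary TEAE, if one was recorded, and nothing in the summaries would show that dosing had stopped.

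**Working it through.** **Step 1: trace each route through the planned outputs.** The routes come from Protocol 7.1.8, 7.1.9 and 10, and the outputs from SAP 7.1, 9.1.4 and Table 3.

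| Route after an AE | In the study-discontinuation rows? | In the other TEAE tables? |
|---|---|---|
| Stops drug, leaves the study, AE recorded as the reason | Yes | Yes |
| Stops drug, is followed, restarts | No: the subject has not left the study | Yes |
| Stops drug, stays enrolled, exits with another recorded reason | No | Yes |

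The second line follows from the text alone and needs no assumed rate. The third depends on how the exit is coded. Protocol 10 puts one reason on the CRF, and early sponsor termination (SAP 10) supplies a competing reason for anyone off drug but still enrolled at that time.

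**Step 2: direction.** Subjects on the second and third routes stopped drug because of an AE and are not counted as having done so. Leaving them out can lower the count but cannot raise it.

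**Step 3: size.** The plan states no figure to reproduce: SAP 3.2 has no sample-size calculation, and neither document gives a rate of drug stops. For scale only, with N = 1081 (SAP 3.3), let p be the assumed share of subjects who stop or interrupt drug for an AE, and f the assumed share of those not counted as study discontinuations.

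Subjects absent = N × p × f. Percentage reported = p × (1 − f).

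| p (assumed) | N × p | Absent at f = 10% / 25% / 50% | Reported at f = 10% / 25% / 50% |
|---|---|---|---|
| 2% | 22 | 2 / 5 / 11 | 1.80% / 1.50% / 1.00% |
| 5% | 54 | 5 / 14 / 27 | 4.50% / 3.75% / 2.50% |
| 10% | 108 | 11 / 27 / 54 | 9.00% / 7.50% / 5.00% |

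For example, 1081 × 0.05 × 0.25 = 13.5, about 14 subjects, and 0.05 × 0.75 = 3.75%. The grid runs from 2 to 54 subjects, or 0.2 to 5.0 percentage points. Both inputs are assumptions, and the relative shortfall is simply f restated. The grid shows what the rows could hide and does not estimate what they do hide.

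**The case against.** The strongest reply is that the gap is narrow, and much of that reply stands.

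- **The events are not lost.** A reader might infer that study discontinuation is the SAP's only tolerability outcome. It is not. SAP 9 covers safety and tolerability together, and 9.1.4 tabulates any TEAE, drug-related TEAEs, maximum severity, SAEs and deaths. What is missing is the fact that the AE stopped treatment.
- **Most permanent stops probably end participation.** Protocol Appendices B and C have no off-drug visit schedule. The exit route is the EoT/ET visit and then a call, which section 7.1.7 times from the last dose. Section 7.1.8 itself refers on to the early-discontinuation section.
- **Coding rules point towards the AE.** Protocol 11.1 requires a withdrawal because of an AE to be recorded as one, and section 10 asks for the most clinically relevant of several reasons. A subject recorded under sponsor termination instead is possible, but the documents do not show that any exists.
- **The data may not support every repair.** For subjects who discontinue, the stop date and the reason for termination are recorded. Neither document shows an action-taken field on the AE form, or interruption and restart dates.
- **No decision rule depends on these rows.** The study is single-arm, open-label and exploratory, with no inferential safety tests planned unless otherwise specified.

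None of this reaches the restart route. Protocol 7.1.8 provides for it, and no planned summary counts it. The descriptive design lowers the stakes but does not make the row complete.

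**Conclusion.** The point holds as a gap in the definition and in the outputs. SAP 2.2.1 leaves withdrawal undefined, and each output showing that an AE ended treatment counts study exits only, although the protocol separates the two events and allows restart. Stops followed by restart are the firm part. Stops followed by an exit under another reason are possible but depend on coding the documents do not show.

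The omission can act only in the drug's favour. Its size is unknown: the 2 to 54 subjects above rest wholly on assumed rates, and for permanent stops the shortfall may be small. Two stronger readings are not supported. One is that a stated fraction of intolerance is being missed, since no rate appears in either document. The other is that study discontinuation is the wrong measure and should be demoted. It is a valid summary that is incomplete on its own, and a subject who restarts and continues is not plainly intolerant.

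**What to change.** 1. In SAP 2.2.1, define withdrawal as covering discontinuation of study drug.
2. In SAP 9.1.4 and Table 3, add TEAE and SAE rows, an SOC/PT table and a listing for TEAEs leading to study-drug discontinuation, including stops followed by restart where these were recorded. Keep the study-discontinuation rows beside them.
3. Add a row for TEAEs leading to drug interruption if the CRF captured action taken or interruption dates. If it did not, state in the CSR that interruptions cannot be counted.

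Before item 2 is programmed, the sponsor should confirm which CRF field ties an AE to the drug stop, because the documents show only the stop date and the reason for termination.

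The cost is SAP wording, a few summary rows, one table and one listing. Sample size, alpha and study procedures do not change. The one downside for the sponsor is that the tolerability figure may look less favourable.
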